Power analysis and estimate of sample size for Experiment 3 [name] (our biostatistician consultant) has performed power analysis based on our pilot study and historical data from the literature. Using nQuery Advisor®, we applied the t-test (ANOVA) for difference of VAS in 2 x 2 crossover design with a 0.05 two-sided significance level. To achieve 80% power of detecting a difference in VAS of 3.0 (the difference between the mean of group BreESTim, $\mu_1=4.0$ and the mean of EStim group, $\mu_2=2.0$) assuming that the Crossover ANOVA \sqrt{MSE} is 3.4 (the Standard deviation of differences, σ_d , is 4.8), the sample size is 24. Assuming an expected dropout rate of 20% given the long-term intervention, we proposed to recruit 30 patients in total for Experiment 3.

D. The data collection and measurement techniques are appropriate and effective

- **Experimental Design**

The overall research design is a within-group, randomized controlled study to compare analgesic effects between EStim and BreESTim (single-session in Exp 1, long-term intervention in Exp 3), between BreESTim120 and BreESTim240 (Exp2). We prefer this within-group comparison because 1) pain, by nature, is a subjective perception, it is difficult to control (physical, social, psychological) multi-factors between two groups; 2) It will be fair that all subjects receive the innovative intervention, which is superior to regular electrical stimulation according to our pilot data; 3) according to our recent BreESTim study in patients with spinal cord injury, the duration of analgesic effect was 15 hours after one-session of BreESTim treatment. An interval of one week for washout should be sufficient for Exp 1 & 2. The washout interval will be 2 weeks for Exp 3. It is our experience with subjects with spinal cord injury that an interval of 7 days is sufficient for subjects to return to their baseline after BreESTim treatment. (Li et al. 2016; Karri et al. 2018b; Li et al. 2018) However, we did notice that one subject with post-amputation PLP had carry-over effect for one month(Li et al. 2012a). We plan to screen these patients with long-lasting carry-over effects. These patients will be excluded from the subject should this happen.

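### Experiment 3 is sized for a VAS difference of 3.0, but the means it cites (4.0 and 2.0) differ by 2.0, for which 24 completers give about 50% power rather than 80%

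*Combined protocol and SAP*

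**What the plan says.** The calculation is in protocol section 4, part C, under the power analysis for Experiment 3. The method is stated as "we applied the t-test (ANOVA) for difference of VAS in 2 x 2 crossover design", "with a 0.05 two-sided significance level". The target is stated as "To achieve 80% power of detecting a difference in VAS of 3.0 (the difference between the mean of group BreESTim", given as 4.0, and the EStim mean, given as 2.0). The parenthesis thus defines the difference as the gap between those two means. The variability inputs are a crossover root mean square error of 3.4 and a standard deviation of differences of 4.8.

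The result is given as "the sample size is 24. Assuming an expected dropout rate of 20% given the long-term intervention, we proposed to recruit 30 patients" in total. Section 5 (Human Subjects) repeats 30 for Aim 3. The 24 is therefore used as the total number of completers across both sequences.

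**The concern.** The sentence gives one quantity two values. It names the detectable difference as 3.0 and defines it by two means that differ by 2.0. Sample size varies with the inverse square of the difference, so moving from 3.0 to 2.0 multiplies the requirement by about (3.0/2.0)² = 2.25 before small-sample correction.

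Experiment 3 carries Aim 3, the two-week comparison of BreESTim with EStim. Section 4, part D says that an improved baseline pain level after the BreESTim course would justify a further clinical trial. Each patient attends 20 sessions. If the stated means are the real planning assumption, the 80% claim is false. A non-significant result would then be about as likely as a significant one even when the assumed effect is true, and it could be misread as evidence of no benefit.

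A smaller point concerns labelling. If 4.0 and 2.0 were VAS pain scores, the lower pain would be on EStim, contrary to the hypothesis. They favour BreESTim only as reductions in VAS, and the paragraph does not say that they are.

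**Working it through.** **Inputs, all from the Experiment 3 power paragraph**

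- Design and test: 2x2 crossover t-test, two-sided α = 0.05
- Root MSE 3.4; SD of within-patient differences σ_d = 4.8
- Difference δ: 3.0 as named, or 4.0 − 2.0 = 2.0 from the means
- Total completers N = 24; dropout 20%; recruited 30

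**Internal checks that agree**

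- σ_d = √2 × 3.4 = 4.81, which matches 4.8.
- 24 / (1 − 0.20) = 30, which matches the recruitment total.

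**Formula**

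For a 2x2 crossover with N patients in total, the standard error of the treatment difference is σ_d/√N and the test has N − 2 degrees of freedom. Power comes from the noncentral t distribution with noncentrality λ = δ / (σ_d/√N), compared with the two-sided 5% critical value.

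**Step 1: reproduce the plan's figure, δ = 3.0**

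- N = 22: SE = 4.8/√22 = 1.023, λ = 2.93, critical t (20 df) = 2.086, power 79.6%.
- N = 24: SE = 4.8/√24 = 0.980, λ = 3.06, critical t (22 df) = 2.074, power 83.3%.

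The smallest even N reaching 80% is 24, so the stated 24 is reproduced with 3.0.

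**Step 2: use the difference between the stated means, δ = 2.0**

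| Completers N | SE | λ | Critical t | Power |
|---|---|---|---|---|
| 24 | 0.980 | 2.04 | 2.074 | 49.7% |
| 30 (no dropout) | 0.876 | 2.28 | 2.048 | 59.6% |
| 46 | 0.708 | 2.83 | 2.015 | 78.9% |
| 48 | 0.693 | 2.89 | 2.013 | 80.7% |

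The smallest even N reaching 80% is 48, which is 24 per sequence. At 20% dropout that is 48/0.8 = 60 recruited.

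**Step 3: smallest difference detectable with 80% power**

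- 24 completers: 2.87
- 30 completers: 2.54

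The stated mean difference of 2.0 is below both.

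**Step 4: could another reading rescue 24 at δ = 2.0?**

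- A paired t-test with 23 df gives 49.8%, and a normal approximation gives 53.2%.
- A one-sided test gives 63%, but the plan states a two-sided test.
- Treating 3.4 as the SD of differences gives 78.6%, but the plan gives that SD as 4.8.

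No reading consistent with the stated inputs brings 24 completers to 80% power for a difference of 2.0.

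**The case against.** The best defence is that the error is a single misprinted mean. Apart from the two means, every figure in the paragraph fits 3.0: 24 is exactly the smallest even total for 80% power, the SD follows from the root MSE, and 30 follows from 24. If a mean should have read 5.0 or 1.0, the difference is 3.0, planned power is 83%, and the sample size needs no change. This stands as a possibility, and the 50% figure is conditional on the stated means being the real assumption.

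The coincidence that 24 is also the exact per-sequence size for a difference of 2.0 is weaker evidence than it looks. It would require both that 3.0 is wrong and that the software output was misread, and the protocol speaks of 30 in total. It is worth a check and is not a finding in itself.

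The labelling point is also partly answered. Aim 3, the outcome description in section 4, part D, and the analysis section all describe the effect as pain reduction on VAS, so a reader can infer that the means are reductions.

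Part of the document just before this calculation was not available for review. It could show which number was intended, but it would not remove the contradiction within the sentence.

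None of this makes 4.0 − 2.0 equal 3.0. Nor do the visible pilot data point to 3.0. In the Experiment 1 pilot, VAS fell by 5.3 − 3.2 = 2.1 after BreESTim and by 4.9 − 4.1 = 0.8 after EStim, a difference of 1.3. That was a single session in 3 patients, so it is no direct estimate for a 10-session course.

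**Conclusion.** The concern holds. The effect size behind Experiment 3's sample size contradicts itself, and the available text does not resolve it. With σ_d = 4.8, a two-sided 0.05 level and 24 completers, power is 83.3% if the difference is 3.0 and 49.7% if it is 2.0. On the means as written, the 80% claim is wrong, and even full retention of 30 gives only 59.6%. These figures take the plan's own SD and its crossover t-test as given. The contradiction is certain. Whether the experiment is actually underpowered depends on which figure is the error, and only the sponsor can say.

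**What to change.** Correct the Experiment 3 power paragraph before the plan is relied on:

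1. Reconcile the detectable difference with the two means, and say whether the means are VAS reductions from baseline.
2. Check the software output to see whether 24 was reported as a total or per sequence, and state which it is.
3. If 3.0 is intended, correct the means. The sample size of 24, with 30 recruited, then stands.
4. If 2.0 is intended, keep 30 recruits and restate power as about 50% at 24 completers, with a detectable difference of about 2.9 at 80% power. Holding 80% power for 2.0 would instead take 48 completers, or 60 recruited at 20% dropout.

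The cost is one rewritten paragraph. No patients are added if power is restated, though the stated power becomes less favourable if 2.0 is the intended difference.

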Specific Aim 1: To examine whether BreESTim could have better analgesic effects on PLP

It is hypothesized that BreESTim has better analgesic effect than EStim, and the analgesic effect is accompanied by elevated electrical pain thresholds. Patients with PLP will receive both BreESTim and EStim in a randomized order with at least 3 days apart. The same amount of stimulation (120 electrical stimuli) at comparable intensities will be used as in our recent studies. According to our preliminary data, we expect that BreESTim has greater pain reduction and longer lasting effect. These results will parallel with increased electrical pain thresholds after BreStim, i.e., desensitization, as compared with EStim.

Specific Aim 2: To examine whether BreESTim-induced analgesic effect is dose-dependent

Similar to taking pain medications, it is hypothesized that there is a dose-response analgesic effect of BreESTim, i.e., an increased "dose" of BreESTim will have a greater impact on reduction of phantom limb pain. Two doses of BreESTim intervention (120 vs. 240 electrical stimuli) will be given to the same amputee with one week apart in a randomized order. According to our preliminary data from 3 subjects, we expect that that a high-dose BreESTim will produce a longer-lasting, but similar degree of pain reduction as compared to a low-dose BreESTim. The findings also suggest a possible cumulative effect of BreESTim, thus leading to a long term effect.

Specific Aim 3: to examine the long-term effect of BreESTim on neuropathic PLP

It is critical to know whether patients will tolerate electrical stimulation and the induced analgesic effect will diminish or the effect will accumulate if patients receive BreESTim repetitively over time, before it is translated into a therapeutic device. It is hypothesized that the BreESTim treatment will produce a greater analgesic effect than the convention electrical stimulation (EStim) treatment in patients after traumatic amputation over a course of 2 weeks (10 consecutive workdays). We will examine the hypothesis by comparing electrical pain threshold and effectiveness in pain reduction between BreESTim and EStim in patients after traumatic amputation of one limb. The analgesic effect will be assessed by pain reduction in visual analog scale and quantitative measurement of electrical sensation and pain thresholds. The effect on general well-being and change in pain medication will be assessed.

4. Research design and methods:

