Location: Neurorehabilitation Research Laboratory at TIRR Memorial Hermann Hospital

C. Each sample population is appropriate and of sufficient size

Pilot data and sample size for Experiment 1 (Aim 1)

In Experiment 1, we plan to use our recent BreESTim and EStim protocols(Li et al. 2013; Li et al. 2014) to compare the induced analgesic effects in patients after traumatic limb amputation. The same experimental protocol for quantitative sensory testing (QST) will be adopted. QST, including mechanical sensation threshold, thermal thresholds (cold/warm sensation, cold/hot pain) and electrical sensation and pain thresholds will be measured in four limbs. In the pilot study we only measured electrical sensation and pain threshold in these areas to estimate the sample size.

We have tested the protocol in 3 patients with PLP after below-the-knee amputation (BKA) (Figure 4). On average, VAS scores decreased from 5.3 to 3.2 after BreESTim. The analgesic effect lasted 16.2 hours. In contrast, VAS scores changed from 4.9 to 4.1 after EStim. The effect lasted 2.0 hours. Electrical sensation detection threshold (EDT) remained similar for both BreESTim (4.9 vs 5.0 mA, pre vs. post) and EStim (4.9 vs. 4.8 mA, pre vs. post). However, electrical pain threshold (EPT) increased from 22.8 to 29.3 mA after BreESTim – a change of 22.1%, in contrast, EPT was very similar before and after EStim (23.4 vs. 23.6 mA, pre vs. post). No difference in tactile and thermal thresholds was found.

[figure not shown]

Figure 4 BreESTim produced a better and longer lasting analgesic effect than EStim in patients with phantom limb pain.

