Power analysis and estimate of sample size for Experiment 1 [name] (our biostatistician consultant) has performed power analysis based on our pilot study and historical data from the literature. A two-way repeated measures ANOVA was used to determine whether any change in VAS score was due to the interaction between INTERVENTION and TIME (i.e. whether one of two interventions is more effective at reducing VAS scores). A power analysis using the G*power computer program (Faul et al. 2007) indicated that a sample of 12 people would be needed to detect a large effect size (> 0.8) with 85% power using a repeated measures two-way ANOVA with alpha at .05, a sample of 14 people would be needed for 90% power. To account for possible subject withdrawal (10%), we plan to recruit 16 subjects. Also to reduce the experimental bias and the order effect, the order of the interventions will be randomized.

Pilot data and sample size for Experiment 2 (Aim 2)

In Experiment 2, the same BreESTim protocol will be used, but at two different doses (120 stimuli vs. 240 stimuli). We have tested the protocol in 4 patients with phantom limb pain after BKA (Figure 5). On average, BreESTim120 and BreESTim240 had similar analgesic effects. VAS decreased from 6.4 to 3.5 after BreESTim120, and from 5.9 to 3.5 after BreESTim300. However, the analgesic effect lasted longer after BreESTim240 (26.1 hours) than after BreESTim120 (14.5 hours). Similar to Experiment 1, these data are from IRB approved study MS-20-1032

analgesic effects were paralleled with similar degrees of change in EPT without changes in other thresholds.

[figure not shown]

[figure not shown]
Figure 5 BreESTim has a dose-response effect on the duration, not the degree of analgesic effects on phantom limb pain.

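### The carry-over exclusion in Section 4.D, on its natural reading, removes patients after period 1 because their relief lasted long, and so biases the duration outcomes

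*Combined protocol and SAP*

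**What the plan says.** Section 4.D (Experimental Design) takes one week of washout as enough for Experiments 1 and 2 and plans two weeks for Experiment 3, relying mainly on experience in spinal cord injury. It then reports an exception from the target population: "we did notice that one subject with post-amputation PLP had carry-over effect for one month". Its response is: "We plan to screen these patients with long-lasting carry-over effects. These patients will be excluded from the subject should this happen".

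The text does not say how long counts as long-lasting, when this is judged, whether excluded patients are replaced, or what happens to their data. None of the seven exclusion criteria in Section 5 concerns carry-over, and Section 6 has no rule for incomplete patients. (Part of Section 4.C, between the Experiment 2 pilot data and the Experiment 3 power paragraph, was not seen.)

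Duration is a stated target. Under Aim 1 (Section 3.B), "we expect that BreESTim has greater pain reduction and longer lasting effect". For the Experiment 1 pilot, Section 4.C reports, for BreESTim and then EStim: "The analgesic effect lasted 16.2 hours. In contrast, VAS scores changed from 4.9 to 4.1 after EStim. The effect lasted 2.0 hours". The Figure 5 caption for Experiment 2 reads: "BreESTim has a dose-response effect on the duration, not the degree of analgesic effects on phantom limb pain". Section 6 tests lasting hours by paired t-test in Experiments 1 and 2, and Section 4.D also measures the effect as VAS reduction multiplied by hours. In Experiment 3 the washout and the follow-up are the same two weeks, and follow-up is a level in the planned ANOVA.

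**The concern.** A patient shows long carry-over only by having long relief. A rule that removes patients for long carry-over therefore selects on the outcome that Aims 1 and 2 compare. If it acts after the first intervention, it takes out the longest responders to BreESTim, mostly from one sequence. Keeping their first-period data would not help, because a paired t-test cannot use a patient who has no second period. In Experiment 3 the rule could also remove some BreESTim-first patients whose benefit persists at follow-up, although Aim 3 asks about long-term effect.

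**Working it through.** The plan gives no figure for the frequency or effect of carry-over, so there is none to reproduce for the main point.

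**1. When can the rule act?** Carry-over is visible only after exposure. Order is randomised (Sections 4.C and 4.D), no BreESTim run-in is described, and the rule is conditional on a future event. This points to exclusion after period 1. It remains an inference, because Section 5 uses the verb screen for clinic screening before enrolment.

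**2. Direction.** Removing patients whose duration exceeds a cut-off cannot raise the mean of those who remain. In Experiments 1 and 3 the loss falls mainly on BreESTim-first patients: pilot relief was 16.2 h against 2.0 h, and Section 4.D expects little or no change after EStim. Long relief after a second-period BreESTim contaminates nothing later, so those patients stay. In Experiment 2 both conditions are BreESTim, and either sequence can lose patients.

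**3. What the pilot data allow.** A mean of 16.2 h in 3 patients caps any one at 3 × 16.2 = 48.6 h. A mean of 26.1 h in 4 patients (240 stimuli) caps any one at 4 × 26.1 = 104.4 h. No pilot patient reached 168 h. If relief were exponential with mean 16.2 h, P(>168 h) = exp(−168/16.2) = 0.00003 and the bias would vanish. If 16.2 h were the mean over all patients, at most 16.2/168 = 9.6% could reach 168 h; larger shares require 16.2 h to describe only patients without carry-over.

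**4. Illustration, Experiment 1.** Assume that a share p has relief lasting to 168 h (the 7-day gap) and the rest average 16.2 h, that EStim gives 2.0 h, and that half receive BreESTim first. The values of p have no source.

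- All kept: (1−p)×16.2 + p×168 − 2.0
- BreESTim-first carry-over excluded: [(1−p)×16.2 + (p/2)×168]/(1−p/2) − 2.0
- Reduction × hours: BreESTim hours × 2.1 minus 2.0 × 0.8, with pilot VAS falls 5.3−3.2 = 2.1 and 4.9−4.1 = 0.8
- Chance of at least one exclusion among 8 BreESTim-first patients: 1−(1−p)^8

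| p | Hours difference, all kept | After exclusion | Too small by | Reduction × hours too small by | At least one excluded |
|---|---|---|---|---|---|
| 1% | 15.7 | 15.0 | 5% | 4% | 8% |
| 5% | 21.8 | 18.1 | 17% | 16% | 34% |
| 10% | 29.4 | 22.2 | 24% | 23% | 57% |
| 20% | 44.6 | 31.1 | 30% | 29% | 83% |

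**5. Illustration, Experiment 2.** If only 240 stimuli carry over (26.1 h against 14.5 h in place of 16.2 h and 2.0 h), the dose difference falls from 13.0, 18.7, 25.8 and 40.0 h to 12.3, 15.2, 19.1 and 27.4 h. If both doses carry over equally and hours are capped at 168, the true difference is 11.6×(1−p) while exclusion gives 11.6 h, which is 1, 5, 11 and 25% too large. Without the cap, exclusion can instead understate the difference if the larger dose lasts longer beyond 168 h.

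**6. VAS and power.** The pilot VAS difference is 2.1−0.8 = 1.3. At p = 20%, with an assumed SD of 2.0, it falls to 1.17 if persistence and VAS benefit correlate 0.43, to 0.99 if they correlate 1, and not at all if they are unrelated. For Experiment 3, the planned n = 24 reproduces: difference 3.0, SD of differences 4.8, 22 degrees of freedom, power 0.83. Losing half of a 20% share leaves 24×0.9 = 21.6 and power 0.79. This uses the stated difference of 3.0, but the stated means, 4.0 and 2.0, differ by 2.0, for which power at 24 is about 0.50.

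**The case against.** The strongest reply is that the text establishes only an undefined rule. Screening could mean asking at entry about earlier BreESTim response. That is fair, and a reader who infers that the plan openly schedules an outcome-based exclusion goes too far. But no such entry criterion is listed and no exposure before randomisation is planned, so the post-period-1 reading is the natural one.

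Second, the size is all assumption. This stands. One might pool the one-month case with the pilot patients ("We have tested the protocol in 4 patients with phantom limb pain after BKA" in Experiment 2, and three in Experiment 1) and claim a prevalence of about one in eight. The documents do not support that. The case was a published report and may have been selected as unusual, its number of sessions is not given, and the pilot groups may overlap. Applying it to a single 120-stimulus session is extrapolation.

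Third, a reader might infer that the rule inflates the case for BreESTim. In Experiments 1 and 3 it does the reverse. The visible sample sizes also rest on VAS rather than hours.

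Fourth, merely keeping these patients is not enough. If persisting relief is then logged as EStim hours up to 168, the Experiment 1 difference becomes 14.9, 17.6, 21.1 and 28.0 h at the four shares, lower than under exclusion. This also stands, and the fix covers it.

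**Conclusion.** The concern holds as a design fault that should be fixed, with medium confidence. On its natural reading the rule removes patients according to the duration outcome, and the planned paired test drops them in any case. The bias runs against BreESTim in Experiments 1 and 3 and has no fixed direction in Experiment 2. The 5 to 30% range for Experiment 1 is illustration only: it rests on unsourced carry-over shares of 1 to 20%, a 168 h duration and balanced order, and it shrinks to nothing if durations have a light tail. The effect on VAS change and power looks smaller, but the documents give no firm bound for it.

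**What to change.** Delete the exclusion from the analysis and keep every randomised patient with all period-1 and follow-up data. Whether such a patient goes on to the second intervention is a separate matter and is not addressed here.

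- **Duration outcomes.** Cap lasting hours and reduction × hours at the same washout interval in both periods and sequences (168 h in Experiments 1 and 2), and state that relief beyond it is not measured. With a gap of at least 168 h this needs no survival method.
- **Carry-over.** Pre-state one rule, the same for both sequences, based on the planned calls and the pre-period-2 VAS. If relief is still present when period 2 starts, set that patient's period-2 hours and VAS to missing, not VAS alone.
- **Analysis.** Replace the paired t-test with a mixed model with treatment, period and sequence, so that period-1 data are used. Report carry-over by sequence and add a period-1-only sensitivity analysis.

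The cost is mostly wording and analysis, plus calls continued until relief ends or the interval closes; the plan gives no stopping point for calls. Standard errors for hours widen: in a simulation with 16 patients and a 5% share, about 9.3 h against 7.4 h under exclusion, with similar signal to noise (21.8/9.3 = 2.3 against 18.1/7.4 = 2.4).

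Detection is imperfect. With assumed repeat-VAS SDs of 1.0, 1.4 and 2.0, a one-sided margin of 1.645×SD wrongly flags 5% and detects a fully persisting 2.1-point fall in only 68, 44 and 28% of patients. This is why the calls and the sensitivity analysis are needed.

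Separately, the minimum gap in Experiment 1 is 3 days under Aim 1 (Section 3.B) and 7 days in Section 4.D. These passages must be reconciled, because the cap depends on the gap.
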